MedStar Diabetes Pathway Ongoing Chart Review Protocol

[name] Principal Investigator

Sub-Investigators

[name] [name]

[name], CRNP, CDE

[name], CRNP

[name]

[name], MS, RD, CDE and [name], MS, RD, CDE
Program Managers

June 1.2016

MedStar Diabetes Pathway Ongoing Chart Reviews

I- Background.

The MedStar Diabetes Pathway (MDP) early pilot program has generated evidence that an innovative technology-enabled “Boot Camp” approach to the delivery of diabetes survival skills education and medication management has a significant impact on glycemic control and healthcare utilization measures. The MDP is a 12 week Diabetes “Boot Camp” technology-enabled intervention which will offer learner-centered survival skills self-management education (DSSE) and algorithm-driven diabetes medications (DM) titration by Endocrinologist-supervised Certified Diabetes Educators (CDE), NPs and PharmDs. The program has been offered at 5 MedStar Medical Group (MMG) Primary Care Practices in FY 15-16 to high risk adults with uncontrolled type 2 diabetes who have a hemoglobin A1C (A1C) level -a marker of average blood glucose (BG) levels in the 2-3 months prior to the time the test is done- which is at or above 9% - considered to be poor control, and 1 or more additional risk factors for poor health outcomes. The program has been well received by MedStar Primary Care Providers and their diabetes patients.

Patients who consent to join the program attend two 1:1 visits with a CDE followed by “virtual” visits via telephone/texting. DSSE is tailored to baseline DM knowledge and medication adherence deficits. An FDA cleared cellular-enabled blood glucose (BG) monitoring system (Telcare BGM®) auto- transmits BGs to a provider dashboard in near-real-time. The CDE reviews BGs and contacts patients at minimum weekly to discuss and make adjustments to DM medications and/or lifestyle, until BG targets are reached. The patient then returns to his/her Primary Care Provider (PCP) with any further ongoing DM management recommendations.

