Ninety-eight (98) patients with uncontrolled type 2 diabetes have completed the MedStar Diabetes Pathway Boot Camp. A1C, a measure of average blood glucose control over the 2-3 months prior to the test being done, was checked at baseline and then after 3 months follow-up. Admissions and resource utilizations were measured for the period 6 months before baseline and then recorded between baseline and 3 months and between 3 months and 6 months. For comparison of A1C improvement, patients were matched to controls at a 1:3 ratio on age, sex, race/ethnicity, insurance group, and baseline A1C. The difference in improvements of A1c between a case and its matched control was tested. Utilization has not yet been captured for controls.

Clinical and Health Resources Utilization Outcomes.

- **A1C Performance.**

Blood glucose control improvement, as measured by change in A1C results is shown below.

Table 1: Change in A1C

	Boot Camp Cases	Control Cases	P value
Baseline A1C (%)	11.35 (1.86)	11.41 (1.71)	0.439
3 month A1C (%)	8.31 (1.52)	9.77 (1.98)	<0.001
Change in A1C (%)	-3.08 (2.01)	-1.64 (1.97)	<0.001
Percent A1C lowering	27%	14%	

The 3.08 % lowering of A1C among Boot Camp patients is highly clinically important. In comparison, most drug trials where A1C lowering is measured, there is typically reduction in A1C of 0.5-1.5% depending upon the drug or drugs being tested¹. Furthermore, a 1% absolute reduction in A1C can be correlated with an approximately 15% reduction in risk for myocardial infarction². The fact that lowering in A1C was also seen among control cases is not completely unanticipated. Per current standard care, when a patient presents with a markedly elevated A1C the physician caring for him/her would implement measures to help improve control which explains the concurrent fall in A1C over time. These results show that the Boot Camp intervention effectively doubled A1C lowering when compared to controls.

- **Health Resource Utilizations.**

Utilization for urgent care visits, urgent PCP visits, hospitalizations, and Emergency Department (ED) visits due to diabetes, taken in the 6 months before the listed time is shown in Table 2.

Table 2. Health Resource Utilizations

	Baseline (n)	3 months		6 months		P value
	Number	Number	% Reduction	Number	% Reduction	
Urgent Care Visits	3	0		0		0.109
Urgent PCP Visits	13	1	91%	1	92%	0.002
Hospitalizations	9	1	88%	3	66%	0.207
ED Visits	18	1	94%	2	88%	<0.001

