- Primary Care Provider willing to have patient enter the program
- Patient is able and willing to participate in the program
- Proficient in English

-AND- one or more of the following high risk characteristics:

- Acute care encounter(s) including) ED visit(s) or hospital admission(s) in the past year with uncontrolled diabetes (BG > 200mg/dL or A1C >9%; severe hypoglycemia = BG <40mg/dL requiring assistance to treat)
- Evidence of low medication adherence as evidenced by no refills since one or more prescribed DM RXs “ran out” (based on last Rx for each DM med and time period was prescribed for on EMR/SureScripts medications list); or any other circumstance that has

been identified by the health care team which indicates poor adherence to prescribed medication.

- Does not meet HEDIS diabetes measures for two or more of: no MA/Cr, no DM retinal exam, no lipid profile
- SBP \geq 140 mmHg
- LDL \geq 100 mg/dL
- Depression diagnosis on problem list (*or depression medication on med list*)
- BMI >32

Exclusion Criteria

- Known history of DKA
- No MedStar PCP visit within past 12 months
- Endocrine or Diabetes Education consult referral order in the past 6 months which resulted in Endo visit(s) or DSME visit(s) documented in chart or self-reported by patient during initial screen
- Active additional medical issues which in the opinion of the care team would preclude concentrating on BG control and/or would predispose to ED visits and/or hospital admits independent of glycemic control, e.g.: severe CHF, severe COPD; severe mental illness.
- Resident of skilled nursing facility, nursing home or receiving home health care services.
- Active cancer in the preceding 3 years excluding nonmalignant basal cell cancer
- Supraphysiologic doses of glucocorticoids (hydrocortisone > 30mg/day; prednisone > 5-6mg daily; dexamethasone > 2mg daily).
- Pregnant or anticipates attempting conception in the following year
- Patient and/or custodial caregiver unwilling and/or unable to participate in program-related activities

The following data will be collected retrospectively from the charts of patients that complete the MDP.

- Demographics
- A1C baseline, at 3 month after baseline visit to assess impact of the pathway.
- Hypoglycemic events (BG<70 and <40) during the 6 months of enrollment in MDP
- Diabetes 2 go Knowledge test
- ED and hospital visits in 30 days and 90 days prior to and after the boot camp
- Referring MedStar Provider satisfaction with intervention

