Statistical Analysis for the MedStar Diabetes Pathway Ongoing Chart Review Protocol. (June 1, 2016).

The study was powered to detect a difference of 0.5 in the change in HbA_{1c} with SD=2 with 80% power at alpha=0.05 with a sample size of 128 in each group (paired t-test). The study reaches 100% power to detect this observed difference (1.6, SD=2.25, post-hoc) with an alpha level of 0.01. Data were summarized using means and standard deviations for continuous variables and frequencies and percentages for categorical variables. Differences in patient characteristics and the unadjusted differences in the outcome measures between the intervention and control groups were tested using linear mixed models, McNemar tests, and conditional logistic models due to matching (Tables 2 and 3). The significance of the comparison between the groups of their respective within group risk change from pre to post-intervention was determined by longitudinal Poisson models that include time and group interactions. Multivariable Poisson regression models adjusted for pre-intervention utilization, baseline HbA_{1c}, age, and sex were used to estimate post-intervention 30-day and 90-day hospital admission and ED visit risk for participants compared to controls (Table 3). The average decrease in HbA_{1c} among men compared to women was examined using a mixed model that included an interaction with sex and group.

Pre-intervention differences between the groups in utilization outcomes were computed and tested using unadjusted Poisson regression models. Analyses were conducted in R 3.1.0 (R Core, Vienna, Austria) (31) and Stata 14 (StataCorp, College Station, TX) (32).

We also conducted an analysis to examine potential for monetization of the intervention benefits from reduced inpatient services to the health system. Based on the expected times of hospitalization per patient in 90 days for both the intervention group and comparison group, estimated by the Poisson regression model, we projected the annual difference in usage of inpatient services between a patient with and without the intervention. The projected change in usage was then multiplied by the expense per diabetes associated hospitalization, which was calculated from the actual claims data of the health system's employee health plan in Year 2017 to be \$25,162.95 per hospitalization.

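### On their plain reading the utilization windows leave out ED and hospital visits during the 12-week boot camp, and no time zero is stated for cases or controls

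*Protocol*

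**What the plan says.** - **Utilization windows.** Protocol section III (data to be collected) lists "ED and hospital visits in 30 days and 90 days prior to and after the boot camp". No item in that list covers ED or hospital visits during the boot camp.
- **Analysis.** The SAP's multivariable Poisson models are used to "estimate post-intervention 30-day and 90-day hospital admission and ED visit risk for participants compared to controls". Its longitudinal Poisson models compare the groups on change from before to after the intervention. Neither statement gives the day on which the later period starts.
- **Programme length.** Protocol section I says "The MDP is a 12 week Diabetes “Boot Camp” technology-enabled intervention". The same section has the educator in at least weekly contact to "make adjustments to DM medications and/or lifestyle, until BG targets are reached", after which the patient goes back to primary care. Section III collects "Hypoglycemic events (BG<70 and <40) during the 6 months of enrollment in MDP". These are three different descriptions of duration.
- **Other anchors.** A1C in section III is tied to the baseline visit: "A1C baseline, at 3 month after baseline visit to assess impact of the pathway". In the pilot (section I), utilization after baseline was "recorded between baseline and 3 months and between 3 months and 6 months".
- **Controls.** Section III describes them as a random sample of health-system patients with elevated A1C, and the SAP treats them as matched. Neither gives them an index date.
- **Savings.** The SAP projects an annual difference in inpatient use from the modelled 90-day hospitalizations and multiplies it by 25,162.95 dollars per hospitalization.

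**The concern.** The Protocol wants the control comparison in order to judge what the programme achieves, on utilization as well as on clinical outcomes. Before and after a 12-week interval most naturally mean before its start and after its end. If so, an ED visit or admission in the weeks when medication is being adjusted is counted nowhere, although the pilot did record that period.

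The comparison also lacks a common clock. A case's later window would open at programme end, an event that a control does not have. If controls were indexed at their elevated A1C (an assumption, since the plan does not say), cases would be observed on days 85-174 and controls on days 0-90, which are different phases after the elevation. The savings figure would then extend to a full year a rate taken from a period without treatment.

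**Working it through.** **1. The plan's own figure.** The documents give no sample size, power or event figure for utilization. The one design figure is for A1C: difference 0.5, SD 2, 80% power, alpha 0.05 (two-sided assumed), paired t-test, 128 per group. The normal approximation is ((1.960 + 0.842) × 2 / 0.5)² = 125.6, so 126 pairs. The noncentral t gives 128 pairs with power 80.15%. The figure reproduces, and this point does not affect it.

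**2. Uncounted days if the later window starts at programme end.** With programme length L, the uncounted share is L/(L + 90) for the 90-day window and L/(L + 30) for the 30-day window.

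| Length L | 90-day window | 30-day window |
|---|---|---|
| 12 weeks = 84 days | 84/174 = 48% | 84/114 = 74% |
| 6 months, about 182 days | 182/272 = 67% | 182/212 = 86% |

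**3. If the window starts at baseline instead.** Nothing is uncounted. But the 30-day window then lies wholly inside a 12-week programme, and 84 of the 90 days (93%) are treatment days, so the label post-intervention would be wrong.

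**4. Events that could fall in the gap.** Inputs: 128 cases (SAP); pilot counts in 98 patients (Protocol Table 2); 6 months taken as 182.5 days and 3 months as 91.25.
- At pre-programme rates: ED 18/98/182.5 × 84 × 128 = 10.8; hospitalizations 9/98/182.5 × 84 × 128 = 5.4.
- At the pilot's rate from baseline to 3 months (1 event of each kind): 1/98/91.25 × 84 × 128 = 1.2 of each.

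The range is therefore about 1 to 11 ED visits and 1 to 5 hospitalizations. The upper end assumes that the programme has no effect and that rates do not fall back after a high baseline.

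**5. Direction.** Taking the pilot text's windows, months 0-3 and 3-6 had 1 and 3 hospitalizations, and 1 and 2 ED visits. Ratios to the pre-baseline rate (half the 6-month count for a 3-month period):
- Hospitalizations: months 3-6 alone 3/4.5 = 0.67; months 0-6 4/9 = 0.44.
- ED visits: months 3-6 alone 2/9 = 0.22; months 0-6 3/18 = 0.17.

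Leaving out the treatment period makes the pilot reduction look smaller. The exact p-values for months 0-3 against 3-6 are 0.63 and 1.0, so the counts settle nothing. The caption of Table 2 also describes 6-month look-backs, which conflicts with the text.

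**6. Savings projection.** If the 90-day estimate is scaled in proportion (the SAP gives no factor), the multiplier is 365/90 = 4.06. One hospitalization per 98 patients in the window becomes 1/98 × 4.06 × 25,162.95, or about 1,041 dollars per patient per year. The 84 uncounted days are 84/365 = 23% of the first year after enrolment.

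**The case against.** The strongest reply is that time zero is undefined rather than set at programme end. The authors use such wording loosely: the text after Table 2 describes the pilot reduction as coming after completion, although the pilot counts began at baseline. A 90-day window from the start would cover all 84 programme days. This stands, and it is why the gap is put here as the plain reading and not as fact.

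A reader might go further and infer that the rate ratio is biased in the programme's favour. The documents do not support that: the few pilot events point the other way and prove nothing.

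Nor can one infer that harm or failure during titration is invisible. The same list collects hypoglycemia during enrolment and A1C at 3 months. Only ED and hospital events could be missed.

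It is also tempting to say that each case's follow-up opens once control has been achieved. The clause "until BG targets are reached. The patient then returns to his/her Primary Care Provider" allows a response-dependent end, but it is one of three descriptions of length. Pilot patients averaged an A1C of 8.31% at 3 months, which does not show that control had been reached, although A1C lags.

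Finally, use after programme end is a legitimate question, and a gap between the earlier and later periods does not by itself invalidate a time-by-group model. That also stands, so the post-programme window need not be demoted.

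None of this removes the problem. From programme end, treatment-period visits are lost and controls have no matching date. From baseline, the windows are mislabelled. With neither reading written down, abstractors could apply either one.

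**Conclusion.** The point holds as a fault in the definition of the utilization windows, and it should be corrected. The 48% (90-day) and 74% (30-day) shares assume that the later window starts at programme end and that the programme lasts 84 days. At the 6-month length they rise to 67% and 86%; with a baseline start they are zero. The number of visits affected is uncertain by several-fold, because it depends on whether pre-programme or on-treatment rates apply. The documents do not establish the sign of any bias, so no claim is made that the planned result favours or disfavours the programme. What they do establish is that no index date is stated for either group, and that the annual savings inherit whichever 90-day window is used.

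**What to change.** **Protocol section III.** Anchor utilization to the baseline visit for cases and to a corresponding index date, set by a written rule, for each matched control. Collect ED and hospital visits for the 30 and 90 days before that date, for days 0-90 and for days 91-180.

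**SAP.** State time zero for both groups. Report the between-group comparison for days 0-90, days 91-180 and days 0-180, alongside any window after programme end. Label each window for what it covers. Base the annual projection on a period that includes treatment, and state the scaling factor.

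**Both documents.** Reconcile the three descriptions of programme length: 12 weeks, contact until glucose targets are met, and 6 months of enrolment.

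**Cost.** Slightly more abstraction and analysis, from charts that are already being reviewed and with no new patient contact. Follow-up to day 180 is only 6 days beyond the 174 that a 12-week programme plus 90 days already requires. The estimated effect may change in either direction.

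### Adding a 12-month prior count of ED visits and admissions would cheaply strengthen the adjusted utilization model, which now has only 30- and 90-day windows to draw on

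*Protocol*

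**What the plan says.** - **Data collected.** The list in the Protocol, section III (Chart Review and Data Collection), includes "ED and hospital visits in 30 days and 90 days prior to and after the boot camp". It gives no longer look-back for utilization.
- **Adjusted model.** The SAP, first paragraph, specifies "Multivariable Poisson regression models adjusted for pre-intervention utilization, baseline HbA_{1c}, age, and sex" to estimate "post-intervention 30-day and 90-day hospital admission and ED visit risk for participants compared to controls". It does not define the window of the utilization covariate; 30 or 90 days is inferred from the protocol's list.
- **Second model.** The same paragraph compares the groups on pre-to-post change with "longitudinal Poisson models that include time and group interactions". The SAP also tests pre-intervention differences in utilization between the groups.
- **Pilot.** In the Protocol, section I, "Admissions and resource utilizations were measured for the period 6 months before baseline", so the planned window is shorter than the pilot's. Utilization had not been captured for pilot controls.
- **Eligibility.** One of several alternative high-risk characteristics for programme patients is "ED visit(s) or hospital admission(s) in the past year with uncontrolled diabetes". Controls are described only as randomly selected patients with elevated A1C.

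**The concern.** Participants and controls are not randomised. Participants must have at least one high-risk characteristic, and Phase 2 extends recruitment to patients with ED or inpatient encounters. No matching requirement is stated for controls on these points. A difference in underlying acute-care use is therefore plausible, although no data in the documents show one.

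In the adjusted model, prior utilization is the only covariate that measures the tendency to use acute care directly. A count over a short window of a rare event is zero for most patients and separates frequent users poorly from the rest. A group difference in underlying use would then remain largely in the adjusted rate ratio. It could also enter the savings projection, which takes 90-day hospitalizations from a Poisson model, annualises them and multiplies by $25,162.95.

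**Working it through.** The documents give no figure for the share of patients without prior use, so there is none to reproduce on this point. The SAP's 128 per group concerns the change in HbA1c and serves below only as a yardstick.

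**1. Pilot rates** (Protocol, section I: 98 patients and Table 2, 6 months before baseline, visits due to diabetes)
- Admissions: 9/98 × 2 = 0.184 per patient-year.
- ED visits: 18/98 × 2 = 0.367 per patient-year.

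**2. Share with at least one event**, Poisson with constant rate: 1 − exp(−rate × days/365.25)

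| Window | Admission | ED visit |
|---|---|---|
| 30 days | 1.5% | 3.0% |
| 90 days | 4.4% | 8.7% |
| 12 months | 16.8% | 30.7% |

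Among 128 patients, a 90-day window finds about 5.7 with an admission (128 × 0.044) and about 11 with an ED visit. A 12-month window finds about 21.5 and 39.

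**3. How much confounding the count removes.** Let each patient's rate follow a gamma distribution with group mean m and variance parameter v, and put a = 1/v. Given k events in a pre-window of T years, the expected rate is (a + k)/(a/m + T). At equal k, with no programme effect, the spurious rate ratio is

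(a/m0 + T)/(a/m1 + T), and the share of log bias removed is 1 − ln(ratio)/ln(m1/m0).

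Assumptions not in the documents: m1 = 2 × m0, with m0 at the pilot rate, and v from 1 to 4. Worked case, admissions, v = 2, 90 days (T = 0.246): (2.722 + 0.246)/(1.361 + 0.246) = 1.85, and 1 − ln 1.85/ln 2 is about 12%.

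| v | Admissions, 90 d | Admissions, 12 mo | ED, 90 d | ED, 12 mo |
|---|---|---|---|---|
| 1 | 1.92 (6%) | 1.73 (21%) | 1.85 (12%) | 1.58 (34%) |
| 2 | 1.85 (12%) | 1.58 (34%) | 1.73 (21%) | 1.40 (51%) |
| 4 | 1.73 (21%) | 1.40 (51%) | 1.58 (34%) | 1.25 (67%) |

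Cells show the spurious ratio left and, in brackets, the share of log bias removed. A 30-day count at v = 2 removes 4% (admissions) and 8% (ED).

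**4. Sensitivity**
- Rates three times the pilot, v = 2: the 90-day count removes 28% (admissions) and 44% (ED), and 12 months removes 61% and 76%.
- Pilot rate assigned to the higher-rate group instead, v = 2: the ratio left is 1.92 at 90 days and 1.73 at 12 months for admissions, and 1.85 and 1.58 for ED.
- A separate simulation for admissions, with true ratios of 1.5 and 2 and v from 1 to 4, gave smaller shares: about 1–20% at 90 days and 9–44% at 12 months. The ordering was the same.

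**5. Both counts together, and the longitudinal model.** Poisson regression on 1.5 million simulated patients (v = 2, 2-fold difference, no programme effect), with counts entered as log(1 + count):
- 90-day count: 1.87 (admissions) and 1.74 (ED).
- 12-month total: 1.59 and 1.40.
- 90-day count plus day 91–365 count: 1.60 and 1.41, practically the same as the 12-month total.
- Ratio of pre-to-post changes, which the time-by-group term estimates: 1.02 and 1.00. The stable difference cancels.

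**The case against.** The strongest reply is that the plan has two utilization analyses. Under the assumptions used here, the time-by-group model is unbiased however sparse the counts, and the SAP also tests baseline utilization differences. This stands. A reader might infer that confounding by prior use passes almost untouched into the plan's utilization result as a whole, but the documents do not support that. The longitudinal model would be exposed to regression to the mean if an acute encounter leads to enrolment, which is a separate matter not modelled here.

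Three further points stand.
- A reader might take it as established that about 95% of patients have no prior admission. The documents contain no such figure. It is an extrapolation for 90-day admissions from nine diabetes-related pilot events. The planned list is not limited to diabetes-related visits, and Phase 2 recruits from ED and inpatient encounters, so actual rates may be higher.
- A reader might infer that a year of utilization data is already in hand. The past-year check is one alternative criterion, concerns encounters with uncontrolled diabetes, and is stated only for programme patients. It need not yield a count, and one PCP visit in 12 months does not show complete capture.
- Replacing the 90-day count with a 12-month count would demote the pre-period data that the longitudinal model needs. A longer count should be added, not substituted.

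The 2-fold difference and the frailty variance are assumptions, and the calculation leaves out matching and the HbA1c, age and sex adjustment. This limits the size of the effect, not its direction: 12 months did better than 90 days in every scenario run.

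**Conclusion.** The concern holds as a specific, inexpensive improvement to one of the two utilization analyses. At pilot rates the 90-day pre-count is a weak adjuster, and a 30-day count is weaker still. With a 2-fold difference in underlying rates and frailty variance 1 to 4, a 12-month count raises the share of log bias removed from about 6–21% to 21–51% for admissions, and from about 12–34% to 34–67% for ED visits. Higher Phase 2 rates would raise both shares.

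The bias would run in whichever direction the groups differ. It affects the adjusted participant-versus-control estimates. It reaches the savings projection only if that uses the adjusted model, since the SAP does not say which Poisson model it means. The HbA1c comparison is not affected. The documents do not show that the groups differ in prior use, so this is a risk and not a demonstrated bias. The undefined covariate window in the SAP is a gap whatever the rates turn out to be.

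**What to change.** - **Protocol, section III, data list:** also collect ED visits and admissions for the 12 months before the index date, abstracted identically in programme patients and controls. Keep the 30- and 90-day counts.
- **SAP, first paragraph:** define the pre-intervention utilization adjustment as two covariates, the 90-day pre-count and the count for days 91–365, each as log(1 + count). Keep the 30- and 90-day pre-counts for the longitudinal model.
- **SAP, savings paragraph:** state which Poisson model supplies the 90-day hospitalizations.

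The cost is a longer date range in a retrospective chart abstraction. Some controls may lack 12 months of MedStar history, so the SAP should say how they are handled. Even with the change, a spurious ratio of about 1.6 (admissions) or 1.4 (ED) would remain in the 2-fold, variance-2 scenario, and the report should acknowledge residual confounding.

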- Patient satisfaction with the MDP

In addition, the clinical team will also compare the clinical and utilization outcomes of patients enrolled in the MDP with those of a randomly selected control group consisting of MedStar

patients with elevated A1C levels. This will be done to allow a better assessment of the impact and effectiveness of the MDP.

Once the data is obtained, it will be de-identified prior to data analysis and reporting. Demographics will be reported as a group, i.e. percentage of patients within a certain age group or geographic area or with a certain type of insurance to insure equal access to the MDP, and help recruit underrepresented groups so they can also benefit from the program.

Data Management

The MedStar Health Research Institute will provide data management services for all aspects of the chart review process, including preparation of the program REDCap database, quality checks of data and developing processes for bringing data into REDCap from available data sources held by system partners which will be leveraged for the program. All data will be de-identified prior to presentation to the Biostatistician for analysis.

Data Analysis and Reporting Plan

Data analysis will be performed by the MHRI Biostatistician. All data will be de-identified prior to submission to the biostatistician for analysis. Results will be reviewed for quality improvement purposes and will also be presented at national meetings. Additionally, one or more manuscripts will be prepared for submission to peer-reviewed journals.

References

1- Management of Hyperglycemia in Type 2 Diabetes: A Patient-Centered Approach

Position Statement of the American Diabetes Association (ADA) and the European Association for the Study of Diabetes (EASD). [Silvio E. Inzucchi](#), MD,¹ [Richard M. Bergenstal](#), MD,² [John B. Buse](#), MD, PHD,³ [Michaela Diamant](#), MD, PHD,⁴ [Ele Ferrannini](#), MD,⁵ [Michael Nauck](#), MD,⁶ [Anne L. Peters](#), MD,⁷ [Apostolos Tsapas](#), MD, PHD,⁸ [Richard Wender](#), MD,⁹ and [David R. Matthews](#). Diabetes Care. 2012 Jun; 35(6): 1364–1379.

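### Controls are not held to the case entry and exclusion criteria and have no index date, so a difference in utilization can come from how the groups were chosen

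*Protocol*

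**What the plan says.** **Control selection.** Protocol section III sets the MDP outcomes against "those of a randomly selected control group consisting of MedStar" patients with elevated A1C. It gives no A1C threshold, source pool, ratio or matching rule. The SAP gives a sample size of "128 in each group (paired t-test") and says group differences were "tested using linear mixed models, McNemar tests, and conditional logistic models due to matching", without listing factors. The only named factors are the pilot's (Protocol, Background): 1:3 on age, sex, race or ethnicity, insurance and starting A1C, used for the A1C comparison.

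**Criteria.** The inclusion and exclusion lists in section III are headed as describing the MDP target population. One inclusion route is an ED visit or admission in the past year. One exclusion removes patients whose other illnesses would cause ED visits or admissions regardless of glycaemic control. Neither list is extended to controls.

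**Windows.** Utilization is collected as "ED and hospital visits in 30 days and 90 days prior to and after the boot camp". Controls attend no boot camp, and no substitute date is given.

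**Analysis.** The SAP plans two utilization models. In one, the "within group risk change from pre to post-intervention was determined by longitudinal Poisson models that include time and group interactions". The other is described as "Multivariable Poisson regression models adjusted for pre-intervention utilization", baseline HbA1c, age and sex. It adds: "Pre-intervention differences between the groups in utilization outcomes were computed and tested using unadjusted Poisson regression models". The cost projection is "Based on the expected times of hospitalization per patient in 90 days for both the intervention group and comparison group", taken from the Poisson model.

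**The concern.** Two of the case criteria act directly on the utilization outcome. The exclusion lowers the cases' expected future visits. Entry through a recent acute encounter, which the Phase 2.0 plan extends to ED and inpatient recruitment, can raise their visits before the boot camp. If controls pass through neither filter, the groups can differ in underlying rate, in recent visits, or in both, before the programme has done anything.

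Each planned model is exposed to one of these. The adjusted post-period model is exposed to a difference in underlying rate. The time-by-group model is exposed to regression to the mean after a qualifying visit. The unadjusted pre-period test can reveal an imbalance but does not correct it. The utilization conclusion and the monetary projection built on it are at stake.

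**Working it through.** **Stated figure.** The SAP's only design calculation reproduces. A paired t-test with 128 pairs, difference 0.5, SD of the paired difference 2 and two-sided alpha 0.05 has power 80.2%. It concerns A1C and implies 1:1 pairs. No power is stated for utilization.

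**Inputs.** Protocol Table 2 gives 9 hospitalizations and 18 ED visits among 98 pilot patients in the 6 months before baseline. Per patient per 90 days this is 9/98/2 = 0.0459 and 18/98/2 = 0.0918. The Background section says control utilization had not been captured. The control-to-case rate ratio m and the spread between patients are therefore assumptions.

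**Check 1: different underlying rates, no programme effect.** Let a case's 90-day rate be μ times a gamma variable with mean 1 and variance v, with k = 1/v. Controls have mean mμ. Given y visits in the pre-window, the expected post-window count is mean × (k + y)/(k + mean). The case-to-control ratio at the same y is

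(k + mμ) / [m(k + μ)].

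This does not depend on y, so conditioning on the pre-count, in whatever form, cannot bring it to 1. As the count gets sparser it tends to 1/m, so a 30-day window helps less than a 90-day one.

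Example, μ = 0.0459, v = 1, m = 2: (1 + 0.0918)/(2 × 1.0459) = 0.522.

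| μ | v | m = 1.25 | m = 1.5 | m = 2 |
|---|---|---|---|---|
| 0.0459 | 1 | 0.809 | 0.681 | 0.522 |
| 0.0459 | 5 | 0.837 | 0.729 | 0.593 |
| 0.0918 | 1 | 0.817 | 0.695 | 0.542 |
| 0.0918 | 5 | 0.863 | 0.772 | 0.657 |

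Simulated fits of the pre-adjusted Poisson model, without the HbA1c, age and sex terms, give about 0.79-0.88, 0.68-0.76 and 0.53-0.67. These agree with the formula within simulation error. The time-by-group ratio stays near 1 here (0.97-1.05), because m multiplies the control counts both before and after.

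**Check 2: recruitment off a recent visit, same population, no programme effect.** Take the pilot hospitalization figure as both the case share with a pre-window visit (s = 0.0459, counting each event as a patient) and the control rate μ. Let p = 1 − [k/(k + μ)]^k be the expected share with a visit. Let E0 = μk/(k + μ) and E1 = [μ − (1 − p)E0]/p be the expected post counts without and with a pre-window visit. The controls' post/pre ratio is 1, so the time-by-group ratio is [sE1 + (1 − s)E0] / (sμ/p).

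- v = 1: p = 0.0439, E0 = 0.0439, E1 = 0.0898; 0.0460/0.0480 = 0.958.
- v = 5: p = 0.0405, E0 = 0.0373, E1 = 0.2491; 0.0471/0.0521 = 0.904.

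So the effect is small, about 0.90-0.96. With the same case share and a control rate of 0.1, the ratio is 1.46-1.89, against the programme. The direction depends on shares that the documents do not give.

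**Form of the pre-count.** When an assumed 25% or 50% of cases enter off a pre-window visit, the adjusted model gives 0.92-1.03 with visits as categories and 0.91-1.43 with a linear count.

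**Carry-over to cost.** Taking 0.046 hospitalizations per 90 days as the expectation without the programme: 0.046 × 365/90 × $25,162.95 = $4,694 per patient-year. A spurious ratio RR projects a false saving of $4,694 × (1 − RR). That is $563-$986 for 0.88-0.79, $1,127-$1,502 for 0.76-0.68, and $1,549-$2,206 for 0.67-0.53.

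**The case against.** The strongest reply is that this is a gap in wording and not a demonstrated bias. Controls can be drawn at random within matched strata. The SAP cites tables that are not supplied, and the matching factors may be described with them. The SAP adjusts for prior utilization, HbA1c, age and sex. An acute encounter is one of seven alternative high-risk routes, with a look-back of a year and not 90 days.

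Much of this stands. A reader might infer a flat contradiction between random selection and matching, but the two are compatible. A reader might also infer that most cases entered off an acute visit and that the time-by-group result is therefore badly distorted. No share is given, and at the pilot hospitalization share with an equal control rate the distortion is slight. Larger distortions need ED and hospital visits pooled, and the SAP describes no pooled outcome. Nor is the A1C power in doubt: the stated paired design delivers it. It is also tempting to name one Poisson model as the right one. Check 1 breaks the adjusted model and leaves the other intact, and check 2 does the reverse for the time-by-group model, so a ranking is not supported.

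What does not stand is the reliance on adjustment. A short pre-count cannot recover a difference in underlying rate, and HbA1c, age and sex are weak stand-ins for severe heart failure, severe lung disease or severe mental illness.

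**Conclusion.** The concern holds in this form: the documents leave controls free of the case criteria and without an index date, and the planned adjustment does not repair a resulting difference in underlying rates. If controls run at 1.25, 1.5 or 2 times the case rate, a programme with no effect would show an adjusted rate ratio of about 0.79-0.88, 0.68-0.76 or 0.53-0.67, including at the pilot hospitalization rate behind the cost projection. These figures rest on assumed multipliers, a gamma-Poisson model with variance 1 to 5, and pilot case counts used as base rates. Those pilot counts cover visits due to diabetes only, whereas section III collects ED and hospital visits without that limit. The documents do not show that controls actually had higher rates. If cases had the higher rates, the error would run against the programme. The visit-based effect on the time-by-group model is a separate exposure of unknown size and direction. This should be fixed before the utilization result or the projected saving is relied on.

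**What to change.** Put one control definition, in the same words, in Protocol section III and the SAP:

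- non-MDP patients who meet the same inclusion and exclusion criteria, as far as charts can establish them;
- an assigned index date for each control, anchoring the 30- and 90-day windows;
- 1:1 matching on the pilot's five factors, consistent with the SAP's paired design.

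Report both planned Poisson models side by side, enter pre-window visits as categories, and state which imbalance each model is exposed to. Matching on a prior acute encounter can be added as a sensitivity analysis.

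The cost is a re-run control query on existing records and a re-analysis. The control pool will be smaller, and the utilization effect may shrink. Willingness to take part and care-team judgement cannot be fully reproduced from charts, so some rate difference may remain. Because the SAP already reports an observed difference, the re-selection must be labelled post hoc.
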